6.4. DRUG MANAGEMENT AND RECOVERY

The Principal Investigator, or someone delegated by him/her, must check the following items each time he/she receives the study drugs (investigational drug and PLACEBO): drug name; quantity; package specification; drug lot number; whether it complies with the quality inspection report; expiration date; whether the conditions during transport comply with the storage conditions; check that the outer packaging of the drug is in good condition; whether the package label is clear; check that the drug labels are well attached; etc.

If storage conditions do not meet the specified requirements (airtight at room temperature) during transport, the batch of trial drugs should be stored under the original storage conditions, segregated from other stored products, and reported to the Principal Investigator, who, together with the sponsor, should judge whether the received batch may be used or not.

After the transfer sheet is completed, it must be properly saved and filed in the folder after the trial.

The Principal Investigator, or someone delegated by him/her, must keep accurate and complete records, including the receipt, accounting, dispensing,

administration, retrieval, return, or loss of the investigational drug. The Principal Investigator must ensure that all experimental drugs are used only by the participants in this study, and that dosage and use must be in accordance with the research protocol.

Unused experimental drugs must be returned to the sponsor or disposed of by incineration, according to SMS Ordinance No. 028, dated October 9, 2014, using the Drug Destruction Form, and must not be transferred to any other research participant.

Regardless of the form of disposal, the documentation generated by the chosen process must be archived along with the documents generated during the research so that they can be audited.

Trial medications should be checked on a regular basis. In case of non-compliance events (wrong code, loss, lost medications, damage, signs of loss of quality, etc.), this should be recorded and reported immediately to the Principal Investigator and the sponsor.

6.5. DRUG INTERACTIONS

Throughout the trial period, the Principal Investigator and his team must record information about the associated diseases and any therapeutic interventions (including drug therapy), surgical procedures etc. relating to the research participants. If possible, this should also include the diagnosis and date of onset of all diseases and the date of symptom relief, as well as the name of the drug involved, the date the drug was taken, and a description of the operation, etc.

6.6. CONCOMITTANT THERAPIES AND PROHIBITED MEDICATIONS

No clinical drug interaction studies have been conducted between AZVUDINE and other experimental anti-SARS-CoV agents. However, in the exploratory studies conducted in China, patients were medicated with experimental anti-SARS-CoV drugs such as arbidol, lopinavir/ritonavir, interferon-2, hydroxychloroquine, osetalmivir, ribavirin, and others, and no AEs occurred and none were attributed to drug

interaction. Clinical trials with HIV-positive patients (GQ-FNC-103 and GC-FNC-104) showed that multiple doses of EFV and TDF significantly increased the degree of FNC exposure in the body. However, the sample size was small and not clinically relevant, so no dose adjustment was needed for FNC combined with EFV or TDF. In addition, another clinical trial (GQ-FNC-201) showed that there was no drug interaction with marketed antivirals for HIV treatment (TDF and EFV), and that the therapeutic effect was comparable to the currently recommended first-line treatment regimen: 3TC + TDF + EFV. All AEs reported in these trials were grade 1 and no additional treatment was required.

The use of some concomitant therapies may interfere with the efficacy, safety, and clarity of the data obtained from the research. There is no evidence that administering AZVUDINE simultaneously with other agents may have no effect or adverse effects, but the information will be added in the protocol.

The Principal Investigator should still review medications prescribed for preexisting comorbidities and evaluate whether these agents may lead to antagonism or synergy with AZVUDINE or jeopardize the safety of the participant, and should modify safety monitoring at his or her discretion if deemed necessary.

It is recommended that individuals who are taking another antiviral for a concurrent infection (e.g., oseltamivir for an influenza virus, lopinavir/ritonavir for HIV, etc.) or immunosuppressive medications for other medical conditions (tocilizumab for rheumatoid arthritis, hydroxychloroquine for lupus, etc.), or experimental medications for COVID-19 not be included in this study. Individuals on alternative treatment should begin treatment with AZVUDINE after the washout period described for each medication:

MEDICINE	WASHOUT
Oseltamivir	>3 days
Lopinavir	7 days
Ritonavir	7 days

INSTITUTO CALZIL		学會
INSTITUTO GALZU PISQUISA, ENSINO, CIÍNCIA E TICNOLOGIA APLICADA	HRH.org	華人四

Tocilizumab	6 weeks
Hydroxychloroquine	14 days

Table 8: Drug washout period

It is planned to collect information on concomitant medications at visits 1 through 17. Concomitant medications should be reported in the appropriate eCRF. Report all prescription medications taken during the study period.

Final guidance on AZVUDINE and possible drug interactions, if available, will be updated in the Investigator's Brochure and in protocol amendments.

6.7. PARTICIPANT MEMBERSHIP

Trial medication adherence is defined as the ratio of the number of actual medications taken to the number of medications that should have been taken during the dose administration period, multiplied by 100. Investigators should record the specific reasons for participants' inadequate adherence in the original medical records and in the eCRF for each visit. The definition of experimental medication adherence failure is: the proportion is less than 80% or greater than 120%.

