 C_{max} in dogs: 85.84-102.55 ng/mL) and 3.099 times lower concentration the dose used in the CHL cell chromosome structure aberration test with the concentration of 7.5 μ g/mL after the 4-hour exposure with or without S9 metabolic activation system.

In this same trial, volunteers receiving 3mg and 4mg of AZVUDINE in a single dose had a plasma exposure of approximately 2.85 and 3.4 ng/mL, respectively. The AUC_{0-t} gradually increased in the 3mg, 4mg and 5mg groups when compared to the 2mg group, with a statistically significant difference between the 4mg and 3mg groups.

Pharmacokinetic data suggest that FNC is rapidly absorbed and slowly eliminated. Total urinary excretion of AZVUDINE increases with increasing dose. Excretion between 0-12h accounted for more than 70% of total excretion in 0-24h.

For the 5 mg dose of AZVUDINE, the average half-life is 13.8h, and it is excreted in the urine in up to 24h.

In the exploratory clinical trials in China, a higher than safety-verified dose (5mg) was used with a dosing regimen of "On Day 1 10mg" in 8 cases at Henan Provincial People's Hospital and yet there were no serious adverse events, serious adverse reactions, major adverse events or death events in the study period. The current dosing design does not use the first dose of 10mg and the current ongoing Phase III clinical trial in China, the dosage is "5mg daily".

In vivo toxicity results from multiple doses of FNC, at high dose in rats (human

equivalent 11.2-56 mg) and dogs (human equivalent 11.16-37.20 mg).

Preclinical trials evaluated much longer administration times than suggested in this clinical trial, leading to a total of the equivalent human dose used in these trials from 116.6 mg (1 month) to 1,088.10 mg (39 weeks).

Animal / human equivalent dose	Animal / Administration time	Total dose used in pre-clinical tests over time
3.72mg	1 month	116.6mg
5.60mg	3 months	504.0mg
3.36mg	6.5 months (26 weeks)	655.2mg
3.72mg	9.75 months (39 weeks)	1,088.1mg

Table 6: Relationship between dose and administration time

The maximum dose of AZVUDINE proposed for this clinical trial is UP TO 70 mg in UP TO 14 DAYS, remembering that the participant can be discharged earlier, reducing the total dose. Long-term exposure to the drug has shown that observable adverse events appear when the dose is exceeded 20-30 times in animals.

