6.2.4. Dose and method of administration

Research participants will be randomized 1:1 to receive the experimental drug or PLACEBO. Each dose of AZVUDINE or PLACEBO will be administered by the research team member qualified and delegated for this role. The administration, date and time,

will be entered into the study eCRF.

AZVUDINE will be administered orally at a dose of 5mg, once daily, while the participant is hospitalized, for up to 14 days of the full course or until two consecutive negative viral load tests are obtained by RT-PCR.

Research participants will be instructed to swallow the medication whole, without breaking, chewing, crushing, or dividing it before ingesting it. The dose should preferably be given at the same time to all participants every day.

The corresponding PLACEBO will be given in equal amounts, at the same time and respecting the same guidelines described above, to the participants who are allocated to the PLACEBO group.

According to the "Clinical study on the postprandial pharmacokinetics of AZVUDINE" (GQ-FNC-105, Henan Genuine Biotechnology Co, Ltd.), conducted in Beijing You'an Hospital affiliated with Capital Medical University, under the responsibility of [name], in the period from Dec-2015 to May-2018, which is one of the reference of studies related to the preliminary stages of clinical development of AZVUDINE (FNC), the incidence of adverse effects observed in both regimens of experimental drug administration (fasting X postprandial) were similar to each other. All AEs were grade 1 in intensity, requiring no therapeutic management measures, thus demonstrating that the FNC administration regimen does not compromise the safety and tolerability of the investigational drug in healthy subjects.

The experimental drug should be administered daily at 8 pm to minimize the risk of falling, since in preliminary studies, it was observed that vertigo (incidence ≥5%) appears to be an AE likely related to FNC. However, no restrictions on meals.

The total course should not exceed 14 calendar days, even if a dose has been missed. The **lost** investigational product, if it occurs, should follow the principle of "whether the lost medication schedule exceeds 1/2 medication interval or not." If the missed medication schedule is within the first 12 hours of the interval between two medications, the missed investigational product can be re-administered normally and

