- Time to normalization of respiratory rate to levels ≤ 24rpm, in room air; [Period: until D15, D21 and D28, approximately 14-30 days]
- Frequency of supplemental oxygenation or non-invasive ventilation; [Period: until D15, D21 and D28, approximately 14-30 days].
- Frequency of invasive mechanical ventilation or extracorporeal membrane oxygenation (ECMO); [Period: until D15, D21, and D28, approximately 14-30 days].
- Proportion of moderate cases that progressed to severe cases requiring intensive care unit (ICU) care; [Period: until D15, D21, and D28, approximately 14-30 days].
- Length of hospital stay; [Period: until D15, D21 and D28, approximately 14-30 days].
- Occurrence of drug interactions; [Period: until D15, D21 and D28, approximately 14-30 days].
- Frequency and intensity of adverse events; [Period: until D15, D21 and D28, approximately 14-30 days].
- Frequency and intensity of unexpected adverse events; [Period: until D15, D21 and D28, approximately 14-30 days].
- Frequency and intensity of serious adverse events; [Period: until D15, D21 and D28, approximately 14-30 days].
- Taxa de mortalidade por todas as causas durante o estudo; [Período: até o D15, D21
 e D28, aproximadamente 14-30 dias]
- Evaluate the tolerability of AZVUDINE (FNC) use at 5mg/day regimen for up to 14 days: [Period: until D15, approximately 14 days].
 - Calculating treatment adherence;

- Total time of use of AZVUDINE (FNC);
- o Proportion of participants who withdrew consent;
- o Proportion of participants who dropped out of treatment.

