VISIT 3-16: PROCEDURE (D1-D14)

The treatment period will start on D1 according to randomization.

The treatment will last up to 14 days, and may be stopped early in case of treatment success (2 consecutive negative RT-PCR tests), participant dropout, or at the Principal Investigator's option, if deemed necessary for the safety of the participant.

For the **Early Termination (ETA)** of treatment, participants should follow the routine from visit 17: End of Treatment (D15), in advance.

The Principal Investigator for the study will be available to answer any questions.

The experimental drug should be administered daily at 8 pm to minimize the risk of falling, since in preliminary studies, it was observed that vertigo (incidence ≥5%) appears to be an AE likely related to FNC. However, no restrictions on meals.

The following procedures will be performed in the V3-16 visits:

- Administration AZVUDINE or PLACEBO daily, at the same time at 8pm, to minimize the risk of falling, since in preliminary studies, it was observed that vertigo (incidence ≥5%) may be an AE likely related to FNC;
- Monitoring drug interactions and AEs on a daily basis;
- Monitoring symptoms, vital signs, oximetry and blood glucose daily;
- Collection of blood samples and respiratory sample (nasal and oropharyngeal swab) for safety and efficacy monitoring tests every 48h);
- CT scan of the lung every 4 days and electrocardiogram on days D1 and D11;

The Principal Investigator may adjust the procedures performed during treatment according to the condition of the research participant and the results of clinical examinations.

VISIT 17: END OF TREATMENT (D15)

At the end of treatment or discontinuation of the investigational drug or PLACEBO, all participants will be required to undergo procedures and tests for safety and efficacy monitoring. The procedures should be performed before discharge from the hospital approximately 24 hours after the administration of the last dose of the investigational drug or PLACEBO, because for the 5 mg dose of AZVUDINE, the mean half- life is 13.8 hours, and it is excreted in the urine within 24 hours.

The treatment will last up to 14 days, and may be stopped early in case of

treatment success (2 consecutive negative RT-PCR tests), participant dropout, or at the Principal Investigator's option, if deemed necessary for the safety of the participant.

The following procedures will be performed at the V17 visit:

- Monitoring drug interactions and AEs;

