11.3. METHOD OF STATISTICAL ANALYSIS

All statistical tests will be two-sided tests.

- If the p-value is ≤0.05, it is considered that there is statistical significance in the test (unless otherwise specified).
- The quantitative indices describe the mean value, standard deviation, median, minimum value, maximum value, lower quartile (Q1), upper quartile (Q3) to be calculated, and the rank indices describe the frequency and percentage of cases.
- Comparison of the two groups under general conditions will be analyzed with appropriate methods according to the types of indicators. Student's ttest or Mann-Whitney test will be used to compare the groups for quantitative data. Chi-square test or Fisher's exact test will be used for categorical data.
- The selected cases should be grouped and at the end of the study determine the three analysis data sets (FAS, PPS, SS).
- For the analysis of demographic information and baseline eigenvalues, the mean value, standard deviation, quartiles, minimum value and maximum value should be calculated for numeric variables. For categorical data, frequency and percentage will be calculated.
- For analysis of medication and drug combination adherence one should calculate the percentage of individuals whose medication adherence is at

least 80-100%. An analysis of the classification of the combination of drugs should also be done.

• For analysis of the primary effectiveness indicator:

Primary Goal

To evaluate the **efficacy and safety of** AZVUDINE (FNC) versus placebo in patients infected with moderate to severe stage SARS-COV-2;

Analysis method:

For the efficacy analysis a logistic regression model will be used with the dependent variable "The proportion of participants with clinical improvement [Period: until D15, approximately 14 days]" and independent variables allocation group, AZVUDINE (FNC) or PLACEBO. For the Safety analysis a logistic regression model will be used with the dependent variable "occurrence of serious adverse events" and independent variables allocation group, AZVUDINE (FNC) or PLACEBO. As a support analysis, with exploratory character, both for efficacy and safety, covariate models will be built as well as other variables that present, in the univariate analysis, statistical significance.

Secondary objective

To evaluate the **clinical outcome** between the AZVUDINE (FNC) group versus placebo in patients infected with moderate to severe stage SARS-COV-2;

Analysis method:

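### Time on study drug is tested between arms as tolerability, although virological success and discharge end dosing by design, so the comparison mixes efficacy with tolerability

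*Protocol*

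**What the plan says.** Section 7.1.2 has a tolerability outcome with four components: adherence, "Total time of use of AZVUDINE (FNC"), the proportion withdrawing consent, and the proportion dropping out of treatment. The synopsis and Section 4 repeat the list. The table in 11.3 assigns the whole block to Student's t, Mann-Whitney and Pearson's chi-square tests. Time of use is nowhere divided by reason for stopping.

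The length of the course varies by design. Section 6.2.4 gives study drug "for up to 14 days of the full course or until two consecutive negative viral load tests are obtained by RT-PCR", and adds that it is discontinued once hospital care ends. Section 7.3 says that treatment "may be stopped early in case of treatment success (2 consecutive negative RT-PCR tests), participant dropout", or on the investigator's decision for safety. Section 9.4 has the primary reason for stopping study medication entered in the eCRF.

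Section 6.7 defines adherence as the "ratio of the number of actual medications taken to the number of medications that should have been taken during the dose administration period", times 100. Failure is when "the proportion is less than 80% or greater than 120" per cent. Section 11.3 instead asks for the percentage of individuals whose adherence is at "least 80-100%. An analysis of the classification of the combination of drugs" (the words after the figure begin the next sentence).

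**The concern.** Time on drug measures tolerability only if people stop mainly because they cannot tolerate it. Here the protocol tells staff to stop when the virus is no longer detected, and again at discharge. Four days on drug can therefore be the best outcome in the trial or a refusal after side effects. If azvudine clears virus faster, its arm will have shorter use for that reason alone. If it is also less well tolerated, the two effects add, and the test cannot separate them. A difference in either direction, or no difference, would say nothing definite about tolerability.

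The adherence ratio has a related but smaller problem. When courses differ in length, the ratio depends on which doses count as due, and 6.7 does not define the dose administration period. The acceptable range also differs between 6.7 and 11.3.

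**Working it through.** The protocol states no adherence or duration result to reproduce. The one figure to check is the maximum course: 5 mg × 14 days = 70 mg, as 5.1.3 states. A full course is thus 14 daily doses. One daily dose counts as one unit below; the ratio is the same in tablets at five a day. Time of use is taken to mean time on assigned study drug in both arms, since two-sample tests are assigned to it.

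**Time of use.** Assume that a fraction f stops at day d for virological success, that all others complete 14 days, and that nobody stops for intolerance. Mean time of use = f × d + (1 − f) × 14. With d = 5 (assumed):

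- f = 20%: 0.2 × 5 + 0.8 × 14 = 12.2 days
- f = 40%: 10.4 days
- f = 60%: 8.6 days
- f = 80%: 6.8 days

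The difference between arms is Δf × (14 − d). For Δf = 20 points this is 0.2 × 9 = 1.8 days at d = 5, 0.2 × 11 = 2.2 days at d = 3, and 0.2 × 3 = 0.6 days at d = 11. Tolerability is identical throughout.

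Conversely, take one arm in which 20% stop at day 5 for success and another in which 20% stop at day 5 for intolerance. Both have a mean of 12.2 days, and the comparison shows nothing although tolerability differs by 20 points.

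**Adherence under two readings of the period in 6.7.**

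| Participant | Own dosing days | Fixed 14 days |
|---|---|---|
| Drops out after 1, 4 or 7 doses, none missed | 100% | 7.1%, 28.6%, 50.0% |
| Drops out, 1 of 4 due doses missed | 3/4 = 75% | 3/14 = 21.4% |
| PCR stop after 3, 5, 9 or 11 doses, none missed | 100% | 21.4%, 35.7%, 64.3%, 78.6% |
| Full course, 2 doses missed | 12/14 = 85.7% | 85.7% |

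The first reading records only how doses were taken while on treatment. The second labels a participant stopped correctly after 11 doses or fewer an adherence failure. Counting doses due up to a stop that the protocol permits avoids both results, but needs a convention for dropouts. Someone who leaves after 4 doses scores 4/14 = 28.6% if the full course would have been due, and up to 4/4 = 100% if a permitted stop was imminent. Serial PCR during treatment is taken while hospitalised (5.1.1), so the truth would usually be unknown.

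**Bands.** Both sections share the 80% floor. They part above 100%: a value of 110% is acceptable in 6.7 and outside the band in 11.3.

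**The case against.** Much can be said for the plan. Withdrawal of consent and dropout from treatment are separate components of the same outcome, adverse events leading to abandonment are listed in the safety analysis in 11.3, and the reason for stopping is recorded. Measuring adherence only while on treatment is respectable and suits a course meant to end early. The protocol attaches no direction to time of use, and one generic list of tests covers all four components. An exact denominator is often left to the SAP.

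This rules out several stronger readings that a reader might infer:

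- *Dropouts are scored as fully adherent.* Section 6.7 does not say that the period is the participant's own dosing days. A 14-day reading gives the opposite result, and even on the own-days reading a missed dose before leaving lowers the score.
- *Failure to persist with treatment is hidden.* It is counted elsewhere in the same outcome.
- *Shorter use is scored as worse tolerability.* No such rule is written.
- *The ratio reaches the primary analysis through the per protocol set.* Section 11.2 asks for strict compliance but names neither the ratio nor a cut-off.
- *The effect can be sized from the 10% dropout allowance or from HOPE-1 conversion times.* The allowance covers leaving the study, not stopping drug. HOPE-1 was an open-label study of 20 patients with mild to moderate disease, and its times ignore this trial's 14-day cap, 48-hour sampling and stop at discharge.

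What the objection does not answer is that the protocol itself places time of use under tolerability and assigns the block tests between groups, while its dosing rule ties that duration to virological response.

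**Conclusion.** The point holds for time of use: as listed and tested, it mixes virological efficacy and discharge with tolerability. The size cannot be derived from the protocol. In the illustration it is 0.6 to 2.2 days per 20-point difference in early success, assuming success stops between day 11 and day 3 and 14 days for everyone else. The undefined adherence denominator is an ambiguity that an analyst would probably resolve sensibly, and the band mismatch matters only above 100%, which should be rare when staff give the doses. All of this concerns one secondary outcome among many. No effect on the primary analysis, the per protocol set or the sample size is shown. It merits changing because the correction is specific and nearly free.

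**What to change.** 1. In 7.1.2 and 11.3 (and in the synopsis and Section 4), report time of use as exposure: descriptively, by arm and by recorded reason for stopping, without a test presented as tolerability.
2. Base the tolerability comparison on the proportion stopping study drug for an adverse event, refusal or withdrawal before the end that the protocol permits. This extends the dropout and withdrawal components already listed. An arm that clears virus faster has fewer days at risk, so show the exposure table beside it.
3. In 6.7, state that the denominator is doses due up to any stop or hold that the protocol itself permits: second negative PCR, D14, discharge, intubation, death, investigator safety stop, pregnancy or laboratory hold. Give an explicit rule for those who refuse or drop out and whose later PCR status is unknown. A safety stop for an adverse event closes this denominator but still counts as an event under item 2.
4. Use one adherence band in 6.7 and 11.3.

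No clinical rule changes and no new data are needed: dose dates and times (6.2.4) and reasons for stopping (9.4) are already in the eCRF. The cost is rewording, slightly more tabulation, and reported adherence that may read slightly lower.
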